3.6.3 Off Protocol Therapy and Off-Study Procedure

Authorized staff must notify the Central Registration Office (CRO) when a subject is taken off protocol therapy and when a subject is taken off-study. A Participant Status Updates Form from the web site (<http://home.ccr.cancer.gov/intra/eligibility/welcome.htm>) main page must be completed and sent via encrypted email to: NCI Central Registration Office at [contact].

4 CONCOMITANT MEDICATIONS/MEASURES

Over the counter medications, such as ibuprofen, may be used to provide relief of local injection site reactions.

5 BIOSPECIMEN COLLECTION

Blood and tissue are tracked at the patient level and can be linked to all protocols on which the patient has been enrolled. Samples will be used to support the specific objectives listed in the treatment protocol(s), e.g., immunologic monitoring, cytokine levels, persistence. Patients who agree to have specimens and data stored to support long-term research efforts within the NCI SB will be consented and enrolled on 03-C-0277.

The amount of blood that may be drawn from adult patients for research purposes shall not exceed 10.5 mL/kg or 550 mL, whichever is smaller, over any eight-week period.

Samples will be ordered in CRIS and tracked through Clinical Trial Data Management system. Should a CRIS screen not be available, the CRIS downtime procedures will be followed. Samples will not be sent outside NIH without IRB notification and an executed MTA.

5.1 SAMPLES SENT TO [name] LAB

- Venous blood samples will be collected in either a 4 mL or an 8 mL SST tube to be processed for serum and stored for future research. Record the date and exact time of draw on the tube. Blood tubes may be kept in the refrigerator until pick up.
- For sample pick up, page [name].
- For immediate help, call [contact] (main blood processing core number) or, if no answer, [contact] (main clinical pharmacology lab number).
- For questions regarding sample processing, contact [name] by e-mail or at [contact].
- The samples will be processed, barcoded, and stored in [name] lab until requested by the investigator.

5.2 SAMPLES SENT TO SURGERY BRANCH CELL PRODUCTION FACILITY

- Venous blood samples will be collected in 8 mL CPT tubes to be processed and stored for future research. Record the date and exact time of draw on the tube. Blood tubes are kept at room temperature until pick up.
- Samples will be picked up by the research nurse or designee and transported to the SB CPF within 24 hours of blood draw.
- The samples will be processed, barcoded, and stored in the SB CPF.

5.3 PRIOR TO EACH VACCINATION

- 8 CPT tubes (8 mL each): SB CPF
- 1 SST tube (8 mL): [name] Lab

5.4 AT EACH SCHEDULED FOLLOW-UP EVALUATION

- 8 CPT tubes (8 mL each): SB CPF
- 1 SST tube (8 mL): [name] Lab

5.5 IMMUNOLOGICAL TESTING

- A variety of tests including evaluation of specific lysis and cytokine release, metabolomic and bioenergetic studies (using Seahorse), intracellular FACS of cytokine production,

ELISA-spot assays, and lymphocyte subset analysis may be used to evaluate the immunological correlates of treatment. In general, differences of 2-3 fold in these assays over the baseline measurement are indicative of true biologic differences.

Note: The collection and analysis of research labs will be monitored by the TIL lab and not by the Center for Cancer Research's data contractor.

5.6 SAMPLE STORAGE, TRACKING AND DISPOSITION FOR SURGERY BRANCH CELL PRODUCTION FACILITY

Blood and tissue collected during the course of this study will follow the Cell Tracking and Labeling System established by the SB CPF. The Cell Tracking and Labeling System is designed to unambiguously ensure that patient/data verification is consistent. The patients' cell samples (blood or tissue) are tracked by distinct identification labels that include a unique patient identifier and date of specimen collection. Cryopreserved blood and tissue samples also bear the date the sample was frozen. All cryopreserved samples are tracked for freezer location and storage criteria. All samples are stored in monitored freezers/refrigerators in 3NW NCI SB laboratories at specified temperatures with alarm systems in place. Serum samples will be sent to the Blood Processing Core (BPC) for storage. Samples will be barcoded and stored on site or offsite at NCI Frederick Central Repository Services in Frederick, MD. All collected samples (blood or tissue) are entered into a central computer database with identification and storage location, and this database is backed up every night.

If, at any time, a patient withdraws from the study and does not wish for their existing samples to be utilized, the individual must provide a written request. Following receipt of this request, the samples will be destroyed and reported as such to the IRB. Any samples lost (in transit or by a researcher) or destroyed due to unknown sample integrity (i.e. broken freezer allows for extensive sample thawing, etc.) will be reported as such to the IRB.

Blood and tissue collected during the course of this study will be stored, tracked and disposed of as specified in protocol 03-C-0277.

5.7 SAMPLE STORAGE, TRACKING AND DISPOSITION FOR DR. [name]'S LAB

5.7.1 Sample Data Collection

All samples sent to the BPC will be barcoded, with data entered and stored in the LABrador (aka LabSamples) utilized by the BPC, and data will be updated to the NCI SB central computer database weekly. This is a secure program, with access to LABrador limited to defined [name] lab personnel, who are issued individual user accounts. Installation of LABrador is limited to computers specified by [name]. These computers all have a password restricted login screen. All [name] lab personnel with access to patient information annually complete the NIH online Protection of Human Subjects course.

LABrador creates a unique barcode ID for every sample and sample box, which cannot be traced back to patients without LABrador access. The data recorded for each sample includes the patient ID, name, trial name/protocol number, time drawn, cycle time point, dose, material type, as well as box and freezer location. Patient demographics associated with the clinical center patient number are provided in the system. For each sample, there are notes associated with the processing method (delay in sample processing, storage conditions on the ward, etc.).

5.7.2 Sample Storage and Destruction

Barcoded samples are stored in barcoded boxes in a locked freezer at either -20 or -80°C according to stability requirements. These freezers are located onsite in the BPC and offsite at NCI Frederick Central Repository Services in Frederick, MD. Visitors to the laboratory are required to be accompanied by laboratory staff at all times.

Access to stored clinical samples is restricted. Samples will be stored until requested by a researcher named on the protocol. All requests are monitored and tracked in LABrador. All researchers are required to sign a form stating that the samples are only to be used for research purposes associated with this trial (as per the IRB approved protocol) and that any unused samples must be returned to the BPC. It is the responsibility of the Principal Investigator to ensure that the samples requested are being used in a manner consistent with IRB approval.

Following completion of this study, samples will remain in storage as detailed above. Access to these samples will only be granted following IRB approval of an additional protocol, granting the rights to use the material.

If, at any time, a patient withdraws from the study and does not wish for their existing samples to be utilized, the individual must provide a written request. Following receipt of this request, the samples will be destroyed and reported as such to the IRB. Any samples lost (in transit or by a researcher) or destroyed due to unknown sample integrity (i.e. broken freezer allows for extensive sample thawing, etc.) will be reported as such to the IRB.

Sample barcodes are linked to patient demographics and limited clinical information. This information will only be provided to investigators listed on this protocol, via registered use of the LABrador. It is critical that the sample remains linked to patient information such as race, age, dates of diagnosis and death, and histological information about the tumor, in order to correlate genotype with these variables.

6 DATA COLLECTION AND EVALUATION

6.1 DATA COLLECTION

The PI will be responsible for overseeing entry of data into an in-house password protected electronic system (C3D), and ensuring data accuracy, consistency and timeliness. The PI, associate investigators/research nurses and/or a contracted data manager will assist with the data management efforts. All data obtained during the conduct of the protocol will be kept in secure network drives or in approved alternative sites that comply with NIH security standards. Primary and final analyzed data will have identifiers so that research data can be attributed to an individual human subject participant. Data will be entered into the NCI CCR C3D database.

All adverse events (AEs), including clinically significant abnormal findings on laboratory evaluations, regardless of severity, will be followed until return to baseline or stabilization of event. Patients will be followed for adverse events from the time the patient receives the investigational agent/intervention to the time of the second follow-up evaluation, or until off-study, whichever comes first.

An abnormal laboratory value will be recorded in the database as an AE **only** if the laboratory abnormality is characterized by any of the following:

- Results in discontinuation from the study

- Is associated with clinical signs or symptoms
- Requires treatment or any other therapeutic intervention
- Is associated with death or another serious adverse event, including hospitalization.
- Is judged by the Investigator to be of significant clinical impact
- If any abnormal laboratory result is considered clinically significant, the investigator will provide details about the action taken with respect to the test drug and about the patient's outcome.

All AEs must be recorded on the AE case report form.

End of study procedures: Data will be stored according to HHS and FDA regulations, and NIH Intramural Records Retention Schedule as applicable.

Loss or destruction of data: Should we become aware that a major breach in our plan to protect subject confidentiality and trial data has occurred, the IRB will be notified.

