3.1.3 Protocol Stopping Rules

New subject enrollment to the protocol will be temporarily halted if any of the following conditions are met, and discussions will be had with the FDA or NIH IRB regarding protocol revisions if applicable:

- If one or more treatment-related death occurs due to vaccination, we will promptly discuss this with the NCI IRB and the FDA.
- Two or more patients develop a grade 3 or greater toxicity at any point in the study not attributable to disease progression (or circumstances unrelated to the study).
 - The following grade 3 reactions commonly associated with immunization **will not** be included in this protocol stopping rule:
 - Pruritus/itching: intense or widespread and interfering with ADL lasting <72 hours
 - Fatigue: severe fatigue interfering with ADL lasting < 72 hours
 - Fever: > 40.0°C for < 24 hours
 - Local lymphadenopathy lasting < 1 week
- If one of the first three patients (or 2 of the first 6 patients, or 3 of the first 9 patients, or 4 of the first 12 patients) develop grade 3 autoimmunity, that cannot be resolved to less than or equal to a grade 2 autoimmune toxicity within 10 days, or any grade 4 or greater autoimmune toxicity.

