3.4.2 Subsequent Follow-up Evaluations

The second follow-up evaluation will take place 1 month (\pm 5 days) after the first follow-up evaluation (Day 56). Subsequent follow-up evaluations will take place every 1-2 months for the first year, and then annually or as clinically appropriate as determined by the PI. As noted in Section **3.4.1**, additional leukapheresis may be performed only at the first follow-up evaluation. It will not be performed at any other post-treatment evaluations.

Note: Patients may be seen more frequently as clinically indicated.

At each scheduled follow-up evaluation, patients will undergo:

- Physical examination, including ECOG
- Vital signs
- CBC w/differential
- Acute Care Panel (sodium, potassium, chloride, bicarbonate, creatinine, glucose, BUN), Hepatic Panel (alkaline phosphatase, AST, ALT, total bilirubin, direct bilirubin), Mineral Panel (albumin, calcium, magnesium, phosphorus), Uric Acid, Creatinine Kinase, Lactate Dehydrogenase, Total Protein
- Lymphocyte phenotyping (TBNK)
- β -HCG pregnancy test (serum or urine) on all females of child-bearing potential (complete at all follow-up evaluations within 4 months after the last vaccine)
- Toxicity assessment, including a review of systems
- Research samples as described in Section **5**
- Imaging studies as performed at baseline to determine tumor response. If clinically indicated, other scans or x-rays may be performed, e.g., brain MRI, bone scan.

Note: Patients who are unable or unwilling to return for follow-up evaluations may be followed via phone or e-mail contact. Patients may be asked to send laboratory, imaging and physician exam reports performed by their treating physician.

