3.6 CRITERIA FOR REMOVAL FROM PROTOCOL THERAPY AND OFF-STUDY CRITERIA

Prior to removal from study, effort must be made to have all subjects complete a safety visit approximately 30 days following the first follow-up evaluation on Day 56.

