7.2.2 NCI-IRB Requirements for PI Reporting at Continuing Review

The protocol PI will report to the NCI-IRB:

1. A summary of all protocol deviations in a tabular format to include the date the deviation occurred, a brief description of the deviation and any corrective action.
2. A summary of any instances of non-compliance
3. A tabular summary of the following adverse events:

- All Grade 2 **unexpected** events that are possibly, probably or definitely related to the research;
- All Grade 3 and 4 events that are possibly, probably or definitely related to the research;
- All Grade 5 events regardless of attribution;
- All serious events regardless of attribution.

Note: Grade 1 events are not required to be reported.

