7.3 IND SPONSOR REPORTING CRITERIA

From the time the subject receives the investigational agent/intervention to the time of the second follow-up evaluation, the investigator must immediately report to the sponsor, using the mandatory MedWatch form 3500a or equivalent, any serious adverse event, whether or not considered drug related, including those listed in the protocol or investigator brochure and must include an assessment of whether there is a reasonable possibility that the drug caused the event. For serious adverse events that occur after the second follow-up evaluation, only those events that have an attribution of at least possibly related to the agent/intervention will be reported.

Required timing for reporting per the above guidelines:

- Deaths (except death due to progressive disease) must be reported via email within 24 hours. A complete report must be submitted within one business day.
- Other serious adverse events as well as deaths due to progressive disease must be reported within one business day

Events will be submitted to the Center for Cancer Research (CCR) at: [contact] and to the CCR PI and study coordinator.

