Storage: Peptides for Pulsing: Lyophilized vials will be stored at -20°C. Reconstituted peptide solutions will be stored at -20°C. DCs will be cryopreserved in Cryostor10 and maintained in vapor phase liquid nitrogen (-140 to -180°C) until used. Poly I:C and R848 are stored at -20°C as lyophilized powders and as reconstituted solutions. Interferon- γ is stored as lyophilized powder at -20°C and as a reconstituted solution at 4°C.

Stability: The peptides, Poly I:C, R848 and DC are stable at the recommended storage temperatures for at least one year. Interferon- γ will be made up fresh for each maturation process. The long-term stability of these vaccine components is under evaluation through an on-going stability testing program.

Route of Administration:

SQ Injection: A total of 1 mL (0.5 to 4×10^7) DCs will be administered as an injection into the deep SQ tissue of a proximal extremity. Injections will preferentially be administered in the

Abbreviated Title: Personalized DC Vaccine

Version Date: March 26, 2018

anterior thigh. Injections will not be given into extremities that have had radical lymph node dissections. The same extremity will be used for each cycle of the peptide loaded dendritic cell vaccine administration.

IV Infusion: A total of (0.5 to 4x10⁷) cells for IV administration will be infused over 20-30 minutes via non-filtered tubing, gently agitating the bag during infusion to prevent cell clumping.

Potential Adverse Events and Risks: The peptide antigens pulsed on to the DCs will be unique to each patient and may mimic portions of natural proteins found naturally throughout the body, there is a chance for the development of autoimmune reactions to cells containing these proteins.

[figure not shown]
Special Handling: The peptides are NOT a cytotoxic or infectious agent and require no special handling. The DCs are a blood derived product. All personnel should treat blood derived products as potentially infectious material. Universal precautions and infection control should be practiced at all times.

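### AE follow-up closes at about Day 86 while the halting rule and IRB table run on, so capture of late non-serious grade 3+ events is not assured

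*Combined protocol and SAP*

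**What the plan says.** Five provisions bear on how long toxicity is collected and counted.

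- **Section 6.1 (Data Collection)** starts AE follow-up at the first vaccine and runs it "to the time of the second follow-up evaluation, or until off-study, whichever comes first". The last two words close the window at that visit even when the patient remains on study.
- **Section 3.1.3 (Protocol Stopping Rules)** pauses enrollment if "Two or more patients develop a grade 3 or greater toxicity at any point in the study", leaving aside disease progression, unrelated causes and a short list of brief grade 3 reactions. A separate autoimmunity clause, tiered over the first 3, 6, 9 and 12 patients, states no time frame.
- **Section 3.4.2 (Subsequent Follow-up Evaluations)** continues visits every 1-2 months in the first year, then annually or as the investigator judges. Each scheduled visit includes "Toxicity assessment, including a review of systems".
- **Section 7.2.2 (continuing review)** asks for a table that includes "All Grade 3 and 4 events that are possibly, probably or definitely related to the research". It sets neither a seriousness condition nor a time limit.
- **Section 7.3 (sponsor reporting)** narrows after the same visit: "For serious adverse events that occur after the second follow-up evaluation, only those events that have an attribution of at least possibly related" to the agent are reported.

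Section 1.1.2 makes vaccine safety a secondary objective. On risks, section 11.2 says "there is a chance for the development of autoimmune reactions to cells containing these proteins".

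**The concern.** A halting rule can act only on events that reach the people applying it. Here the rule spans the whole study, but the section that defines AE follow-up stops early. The visits that could detect a late event continue, so the clinical information would exist. What is missing is a clear instruction to record it as an AE.

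The exposed case is specific: a new event of grade 3 or higher that does not meet the seriousness criteria in 7.1.5, first seen after the second follow-up, in a patient still on study. Grade 3 alone is not a seriousness criterion there. Because progression takes patients off study (3.6.2), those still on study are mainly patients without progression, including any responders.

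Two things are at stake: whether the halting rule can work as written during an accrual period that section 8.2 puts at about 6 years, and whether the safety summary in 8.4.4 is complete for patients followed longest.

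**Working it through.** The plan gives no figure to reproduce on this point. The check is date arithmetic, then a trace of one event through the provisions, then an illustration under assumed rates.

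**Inputs.** First follow-up: Day 56 ±5 (3.4.1). Second follow-up: one month ±5 days later (3.4.2). Fourth vaccine: nominal Day 42 (3.2). Later visits: every 1-2 months in year 1 (3.4.2). Assumptions: a 30-day month, 61 days for two months, and year 1 ending on Day 365 from the first vaccine.

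**Step 1: where the window closes.**
- Nominal: 56 + 30 = Day 86. A 28- to 31-day month gives Day 84 to 87.
- Earliest: (56 − 5) + (30 − 5) = Day 76. Latest: (56 + 5) + (30 + 5) = Day 96.
- Time since the fourth vaccine: 86 − 42 = 44 days.
- Section 3.6 agrees on timing; it describes a "safety visit approximately 30 days following the first follow-up evaluation on Day 56".

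**Step 2: what lies beyond it, for a patient who stays on study all year.**
- Days outside the window: 365 − 86 = 279, and 279/365 = 76%.
- Scheduled toxicity assessments outside it: 279/30 gives 9 whole intervals; 279/61 gives 4. So about 4 to 9.

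**Step 3: trace one event.** Take a new, non-serious, possibly related grade 3 event found at a visit in month 5, with the patient still on study.

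| Provision | Does it reach this event? |
|---|---|
| 3.4.2 toxicity assessment | Yes, it would be seen |
| 6.1 AE follow-up | No, the window has closed |
| 7.3 sponsor reporting | No, it is not serious |
| 7.2.2 IRB table | Yes, by its terms |
| 3.1.3 grade 3+ clause | Yes, by its terms |

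Two provisions require the event to be counted, and the one that governs AE follow-up does not require it to be collected.

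**Step 4: how much the halting rule could depend on this.** The documents give no early or late event rate, so these are assumptions. With n patients and a per-patient rate p, the chance that two or more are affected is 1 − (1 − p)^n − n·p·(1 − p)^(n−1). Use p = early rate if only events up to about Day 86 count, and p = early + late rate if later ones count too. The sizes are 42 patients (2 × 21, first stage of both cohorts) and 86 (the maximum in 8.2).

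| Early rate | Late rate | n = 42: early only → all | n = 86: early only → all |
|---|---|---|---|
| 1% | 1% | 0.07 → 0.21 | 0.21 → 0.52 |
| 1% | 2% | 0.07 → 0.36 | 0.21 → 0.73 |
| 2% | 2% | 0.21 → 0.51 | 0.52 → 0.86 |

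These differences are upper bounds for the assumed rates: every patient is taken to stay on study long enough to have a late event, and every late event is taken to be missed. If the late rate is zero, the difference is zero.

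**The case against.** The strongest reply is that the protocol has other routes for a late event, and much of that reply stands.

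- Section 6.1 limits the period of AE follow-up; it does not forbid recording something found later. The same section sends every AE to the case report form, and 6.1.1 exempts nothing from routine recording.
- The halting rule is not tied to database entries. Section 7.5.1 has the investigator review AE data for each patient and report safety concerns to the IRB immediately. Section 7.2.1 covers unanticipated problems within 7 days.
- Related serious events remain reportable under 7.3, and 7.1.5 allows important medical events to be classed as serious. Events that began inside the window are followed until they return to baseline or stabilize.
- The numbered autoimmunity tiers end at the first 12 patients, although later grade 3+ autoimmunity still falls under the general clause.

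A reader might therefore be tempted to go too far and infer that late events are never recorded or counted. The documents do not support that: no passage bars it, and 7.2.2 presupposes that related grade 3-4 events are known. Nor do they support saying that the safety results are biased by a known amount, or that responders are the group most prone to delayed autoimmunity.

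The reply does not close the gap, however. Section 6.1.1 is a subsection of 6.1 and sets no period of its own. Section 7.5.1 reviews data without saying how long they are collected. Section 7.2.2 is a summary that needs collected data. If these sections are read as keeping collection open, they conflict with the cut-off in 6.1, so reconciliation is needed on either reading.

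**Conclusion.** The point holds as an inconsistency between sections. AE follow-up ends at nominal Day 86 (76 to 96), about 44 days after the fourth vaccine, while the halting rule and the IRB table carry no such limit and later visits still assess toxicity. A new, non-serious grade 3 or higher event in a patient still on study after that visit is not assured to reach the case report form, the halting rule or the safety results.

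Its practical size is unknown, since the documents give neither a late-event rate nor the time patients are expected to stay on study. The 76% and the 4 to 9 assessments describe only a patient who remains for a full year, and the probabilities rest on assumed rates. Patients already off study are not part of the point, because 3.6.2 ends data collection for them. The response endpoint is unaffected. This should be corrected, but it does not undermine the design.

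**What to change.** Reconcile 3.1.3, 3.4.2, 6.1, 7.2.2 and 7.3 so that the AE collection window covers the period that the halting rule and the IRB table already state.

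- In 6.1, after the second follow-up and while the patient is on study, keep AE recording open for events of grade 3 or higher that are at least possibly related to the research. Use the toxicity assessments that 3.4.2 already schedules.
- In 3.1.3, add a cross-reference saying that events recorded in this way are among those the rule considers. Leave its thresholds, grades and exclusions unchanged, and do not bring lower-grade autoimmune events into it.
- Check that the attribution wording in 3.1.3 (not due to progression or unrelated circumstances) and in 7.2.2 (at least possibly related) select the same events.

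The cost is a wording amendment and a small amount of data entry at visits that already take place; no new visit or test is needed. Reported late toxicity may be slightly higher. Because the later period would collect a narrower set of events, the safety summary should show the two periods separately.
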